2.6 Intervention

All the participants are requested to refrain from consuming tea/alcohol/coffee and smoking on the examination day. Besides, exercise and food is also forbidden within one hour before the LDF examination.

2.6.1 Location of the acupoints

- (1)LU9: On the anterolateral aspect of the wrist, between the radial styloid process and the scaphoid bone, in the depression ulnar to the abductor pollicis longus tendon.
- (2)LU5: On the anterior aspect of the elbow, at the cubital crease, in the depression lateral to the biceps brachii tendon.
- (3)HT7: On the anteromedial aspect of the wrist, radial to the flexor carpi ulnaris tendon, on the palmar wrist crease.
- (4)HT3: On the anteromedial aspect of the elbow, just anterior to the medial

epicondyle of the humerus, at the same level as the cubital crease.

2.6.2 Examination environment

The environmental temperature is within 24–26°C during the entire measuring period. The relative humidity will be controlled between 40% and 50%. There is no direct sunlight and obvious air convection in the room.

2.6.3 Procedures for LDF examination and moxibustion intervention

A four-channel LDF (PeriFlux System 5000, Sweden) will be used to measure the microcirculatory characteristics of meridian phenomena for the Heart and Lung meridians, which could monitor 4 measuring sites simultaneously. The participants will be asked to stabilize for 15 minutes in a supine position in the experimental room before formal examination. They will be informed to keep silent and normal breath and avoid limb movement during the whole measuring period. The probes will be left at relevant measuring sites. Blood flow curve will be recorded constantly using Perisoft software (PeriFlux, Sweden). Perfusion units (PU) of microcirculatory flux in the measuring sites will be calculated by the software [PU = concentration of moving blood cells (CMBC) × velocity (V)].

(1) Healthy control group and COPD group

The probes will be left at 4 measuring acupoints, which include Shenmen (HT7) and Shaohai (HT3) of the Heart meridian, Taiyuan (LU9) and Chize (LU5) of the Lung meridian. The blood flow curve and PU will be recorded for 5 minutes.

(2) Healthy intervention group

Two sessions of moxibustion intervention will be performed in the Heart meridian and Lung meridian successively. The washout period between the two sessions is at least one day.

1) Intervention in the Heart meridian: By igniting the moxa stick and inserting it into a homemade moxibustion holder to adjust the appropriate angle and height, moxibustion will be performed above Shaohai (HT3) of Heart meridian for 15 minutes. During moxibustion, the probes will detect the blood flow curve and PU in four sites in two meridians, which include Shaohai (HT3) of the Heart meridian, the midpoint of the Heart meridian along the left forearm (i.e. the midpoint of the line

between HT3 and HT7), Chize (LU5) of the Lung meridian, and the midpoint of the Lung meridian along the left forearm(i.e. the midpoint of the line between LU5 and LU9). The measuring time points include 5 minutes before moxibustion, 15 minutes during moxibustion and 5 minutes after stopping moxibustion.

2)Intervention in the Lung meridian: The moxibustion acupoint is Chize (LU5) of the Lung meridian. The LDF examination, moxibustion procedure, measuring sites and time points are the same as 1).

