ID: 2019ZY004-MERIDIAN

Research title:

A study on the microcirculatory characteristics of meridian phenomenon for the heart and lung meridians based on patients with chronic obstructive pulmonary disease

Date: March 25, 2019

Study Protocol

Part1. Study introduction and objectives

(1) Brief introduction

This study will include 40 patients with chronic obstructive pulmonary disease (COPD), and 80 healthy volunteers. Laser doppler examination will be adopted to assess the microcirculatory characteristics of meridian phenomena and investigate the site specificity for the meridian-visceral association and surface-surface association between two specific meridians.

(2) Study objects

1) This study aims to detect the microcirculatory characteristics of meridian phenomena using laser doppler flowmetry(LDF). Thus, the biological characteristics of meridian phenomenon could be presented objectively in a scientific methodology.

2) This study aims to investigate the site specificity for the meridian-visceral association and surface-surface association between two specific meridians.

Part2. Study program

1.Study subjects

The subjects of this study include two kinds of participants, which includes healthy volunteers and patients with COPD.

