2.4 Grouping

A total of 120 participants will be divided into the healthy control group, COPD group and healthy intervention group., with 40 in each group respectively.

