2.6.4 Concomitant treatments

During the study period, all the participants in the COPD group will maintain their previous treatment regimen. If additional medications or other treatments are used during the study period due to any reasons, the details (e.g. the name, administration time and dosage of the medication) should be documented.

Besides, participants in the healthy control group and healthy intervention group should not take any medications during the full study period. If drugs or other treatments are adopted due to sudden diseases, relevant information should be documented and researchers will evaluate whether they should be withdrawn from the study.

3. Outcome measurement

Primary outcomes will be blood flow curve and blood perfusion units (PU) of relevant sites along the Heart and Lung meridians.

4. Safety evaluation

Adverse events (AEs) that occur during the trial will be recorded and assessed by the investigators during each examination session and at each visit next time. If serious AEs occur, the researchers should report them to the principal investigator and ethics committee immediately, who will make a decision on whether the participant should be withdrawn from the study.

5. Ethical approval and study registration

Ethics approval (approval document No: ZCMU-KY-2019-042, April 29, 2019) was obtained from the Ethics Committee of Zhejiang Chinese Medical University. The purpose, contents and potential risks of the research will be fully explained to the

participants and their families. All participants will complete the informed consent form before participating in the study. All participants' personal and disease information will be kept confidential.

6. Quality control

(1) The trial protocol has been modified according to suggestions from experienced acupuncturists.

(2) Before the trial, all researchers who enroll participants and collect data must attend a series of training sessions. These training sessions will ensure that all research staff involved fully understand the trial protocol and standard operating procedures (SOP).

[figure not shown]
(3) SOP of the examination method is designed before the trial.

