2.3 Statistical analysis

All data in this study will be analyzed by a blinded statistician. Independent sample T test and Chi-square test (χ^2 test) will be used for numerical variables and categorical variables, respectively. When the distribution of variables is abnormal, a non-parametric test will be selected. A P value < 0.05 will be considered statistically significance.

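### With the Heart session always first and the Lung session always second, the HT3-versus-LU5 heating comparison cannot be separated from session order

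*Combined protocol and SAP*

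**What the plan says.** Section 2.6.3 (2) of the protocol gives the healthy intervention group two moxibustion sessions: "Two sessions of moxibustion intervention will be performed in the Heart meridian and Lung meridian successively". Item 1) heats HT3 on the Heart meridian. Item 2) heats LU5 on the Lung meridian, and "The LDF examination, moxibustion procedure, measuring sites and time points are the same as 1". On spacing, "The washout period between the two sessions is at least one day". Each session has its own baseline: "The measuring time points include 5 minutes before moxibustion, 15 minutes during moxibustion and 5 minutes after stopping moxibustion". Section 2.4 sets the group sizes, "with 40 in each group respectively".

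No readable section randomises, alternates or balances the order of the two sessions. Two places that might do so cannot be read: the flow diagram (Part 2, section 7), and the examination procedure that Part 2, section 6 mentions only by saying "SOP of the examination method is designed before the trial".

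The second objective in Part 1 reads: "This study aims to investigate the site specificity for the meridian-visceral association and surface-surface association between two specific meridians". Part 3, section 2.3 names "Independent sample T test and Chi-square test", with a non-parametric alternative. It has no paired, period or sequence term and names no contrast for this group.

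**The concern.** If everyone has Heart first and Lung second, heated meridian and session number are the same variable. Volunteers may respond differently to heat the second time through familiarity, habituation or residual effect. In a comparison of HT3 heating with LU5 heating, such a change would appear as a meridian difference, or would cancel a real one. The same holds for one site compared between sessions, which recording identical sites in both sessions invites.

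The pre-moxibustion recording helps only in part. Change from baseline removes a different resting level on the second day, but not a different response to heating.

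The objective concerns two specific meridians and perfusion at these sites is a primary outcome, so this comparison is one the authors could easily make. Nothing in Part 3 steers the analyst away from it.

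**Working it through.** The plan gives no effect size, SD or power, so there is no figure of its own to reproduce. The check has two parts: what the design can estimate, and how large the error could be.

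**Inputs.** From the documents: n = 40 (2.4); Heart then Lung (2.6.3); significance level 0.05 (Part 3, 2.3), taken as two-sided. Assumed: session-2 shift d = 0.2, 0.3 or 0.5 SD; correlation ρ = 0.3, 0.5 or 0.7, equal across all of a person's measurements; no true meridian difference.

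**Estimability.** A model with 40 person terms, one session term and one heated-meridian term has 42 columns.
- All 40 Heart-first: rank 41, and heated meridian correlates 1.0 with session. The effect is not estimable.
- 20 Heart-first, 20 Lung-first: rank 42, correlation 0. The effect is estimable with variance 2/40 = 0.05 times the within-person residual variance.
- Own-versus-other contrast (heated versus unheated meridian) with additive site and session terms: full rank even under the fixed order. Adding a site-by-session term makes it deficient (rank 4 of 5 columns).

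**Overall HT3-versus-LU5 comparison, fixed order.** For a paired test the noncentrality is d√(n / [2(1−ρ)]) on 39 df. At d = 0.3, ρ = 0.5 this is 0.3 × √40 = 1.90, giving 45.7% false positives.

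The independent-sample test uses a standard error of √(2/40) = 0.224 SD where the true one is √(2 × 0.5/40) = 0.158 SD, so it is conservative for small shifts but still fails for large ones. Its rates are simulated (20,000 trials per cell).

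| ρ | Independent t, d = 0.2 / 0.3 / 0.5 | Paired t, d = 0.2 / 0.3 / 0.5 |
|---|---|---|
| 0.3 | 10% / 23% / 61% | 18% / 35% / 74% |
| 0.5 | 7% / 19% / 64% | 23% / 46% / 87% |
| 0.7 | 3% / 13% / 67% | 36% / 67% / 98% |

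With order randomised 20:20 and a period-adjusted test, the rate is 5% in all nine cells.

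**Own-versus-other contrast, fixed order.** Take one Heart site H and one Lung site L: C = (H1 − L1) − (H2 − L2), with SD 2√(1−ρ).
- A shift common to both sites cancels, and the rate stays at 5%.
- If only the Heart site's response shifts, the noncentrality is d√n / [2√(1−ρ)]. At d = 0.3, ρ = 0.5 this is 0.3 × 6.325 / 1.414 = 1.34, giving 26%. For d = 0.2/0.3/0.5 the rates are about 14%/26%/59% at ρ = 0.5, 12%/20%/46% at 0.3 and 20%/40%/81% at 0.7. Under 20:20 they return to 5%.
- If instead the shift follows whichever site was heated before (carry-over), 20:20 does not help: the pooled contrast stays at about 14%/26%/59% at ρ = 0.5.

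**Session 1 only.** Under the fixed order, this own-versus-other contrast assumes that HT3 and LU5 react alike. If they differ inherently by 0.2/0.3/0.5 SD, it is falsely significant in 23%/46%/87% of trials (ρ = 0.5). Comparing H − L between two randomised sequences (20 versus 20) gives 5%.

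**The case against.** The best counter-argument has four parts.

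- **The order is inferred.** The text says the sessions follow one another. It does not say which comes first for every participant, and the flow diagram and examination procedure cannot be read. This stands as a limit on certainty. Fixed order is still the natural reading, and if the order is varied, the protocol should say so and the analysis should use it.
- **The exposed comparison is not a stated one.** Site specificity is more naturally tested by comparing the heated with the unheated meridian within a session, which withstands any shift common to all sites. This also stands: the harm depends on which contrast is chosen. Part 3 leaves that choice open.
- **Existing controls narrow the problem.** Each session has its own baseline recording, the plan requires 15 minutes of supine rest, room conditions are controlled, and there is a washout. These deal mainly with resting level. They do not rule out a changed response to heat, although the documents give no evidence that one occurs.
- **Randomising order does not cure everything.** Carry-over at the previously heated site distorts the pooled own-versus-other contrast equally under either design. That is correct, and protection there still rests on the washout. Only the session-1 analysis avoids it.

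Also, by the test the plan names, a small shift of 0.2 SD gives only 3% to 10% false positives.

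**Conclusion.** The concern holds on the plain reading of section 2.6.3 (2). The overall HT3-heating versus LU5-heating comparison, and any one-site comparison across sessions, are completely aliased with session order in all 40 volunteers, and this cannot be undone after data collection. The aliasing is a property of the design and needs no assumption beyond the fixed order. The false-positive rates do rest on assumed shifts and correlations and show a range only.

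The damage is limited. Own-versus-other contrasts are biased only if particular sites change their response in session 2, and the COPD versus healthy control comparison is untouched. It does not invalidate the intervention arm, but it should be corrected because the remedy costs so little. Confidence is medium, because the order is inferred and the contrast is unnamed.

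**What to change.** - **Section 2.6.3 (2):** state the session order and randomise it 1:1 from a computer-generated list (20 Heart-first, 20 Lung-first). Leave procedures, durations and washout as written.
- **Part 3, section 2.3:** for this group, analyse change from each session's pre-moxibustion perfusion in a within-person model with period and sequence. Name the contrast: own versus other meridian, overall HT3 versus LU5, or both.
- **Sensitivity analysis:** using session 1 only, compare the Heart-site-minus-Lung-site difference between the two sequences. This is free of carry-over.

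If sessions have already been run in one order, restrict inference to own-versus-other contrasts and report the limitation.

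The cost is a 40-line list and a slightly longer analysis, with no added visits or participants. Power for a 0.5 SD overall difference at ρ = 0.5 is 87% either way; period adjustment uses one degree of freedom. The session-1 own-versus-other check has 87% power for 0.5 SD (74% at ρ = 0.3, 98% at 0.7). A session-1 overall HT3-versus-LU5 comparison has only about 34% and should not be relied on.

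### The plan does not stop direct heating at the moxibustion acupoint, itself a recorded primary-outcome site, from being read as a same-meridian response

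*Combined protocol and SAP*

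**What the plan says.** Part 1 sets out to "investigate the site specificity for the meridian-visceral association and surface-surface association between two specific meridians". The surface-surface part rests on the healthy intervention group, who have two moxibustion sessions (section 2.6.3).

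- Heart session: "moxibustion will be performed above Shaohai (HT3) of Heart meridian for 15 minutes". Recording covers four sites: "the probes will detect the blood flow curve and PU in four sites in two meridians, which include Shaohai (HT3) of the Heart meridian", the Heart forearm midpoint, LU5 and the Lung forearm midpoint.
- Lung session: "The moxibustion acupoint is Chize (LU5) of the Lung meridian", and "The LDF examination, moxibustion procedure, measuring sites and time points are the same as 1".
- Recording periods: "5 minutes before moxibustion, 15 minutes during moxibustion and 5 minutes after stopping moxibustion".

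Section 3 defines the outcome: "Primary outcomes will be blood flow curve and blood perfusion units (PU) of relevant sites along the Heart and Lung meridians". It does not say which sites are relevant to which question. SAP 2.3 names an independent-sample t test for numerical variables, or a non-parametric test if the distribution is not normal, at P < 0.05. It names no contrast between sites, no time window and no rule for the heated acupoint. No sham heat, off-meridian control site or skin-temperature measurement is described.

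**The concern.** In each session one of the two treated-meridian probes is at the point being heated, and neither probe on the other meridian is directly under the moxa. A perfusion change at the heated point may simply be the skin's response to heat, so it cannot show an association with anywhere else. If that point enters a same- versus other-meridian comparison, alone or averaged with its midpoint, the comparison is unbalanced in the direction the study hopes to find. Running both sessions does not cancel this, because the heated point moves with the treated meridian. At stake is the surface-surface half of objective 2: apparent specificity could arise where meridians play no part.

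**Working it through.** **No plan figure to reproduce.** Section 2.2 gives the sample size without power, effect size or SD. The counts agree: 3 × 40 = 40 + 80 = 120.

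**Which sites are heated and recorded (section 2.6.3)**

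| Session | Moxa above | Treated-meridian sites | Other-meridian sites |
|---|---|---|---|
| Heart | HT3 | HT3, Heart midpoint | LU5, Lung midpoint |
| Lung | LU5 | LU5, Lung midpoint | HT3, Heart midpoint |

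The elbow acupoint of the treated meridian is always the heated one. The two midpoints are never directly under the moxa.

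**Illustration.** From the documents: n = 40 and significance level 0.05 (two-sided assumed). Assumed: percent change in PU has the same SD at each site, between-site correlation ρ = 0.3, heating raises the heated point by r, and nothing happens at the other three sites. Let S be the mean of the two treated-meridian sites and O the mean of the other two.

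- Expected S − O = r/2
- Var(S) = Var(O) = SD²(1 + ρ)/2
- Var(S − O) = SD²(1 + ρ) − 2ρSD² = SD²(1 − ρ)

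*Independent-sample t test (named in SAP 2.3).* It uses standard error SD√((1 + ρ)/n), while the actual one is SD√((1 − ρ)/n). With critical value 1.991 (78 df):

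rate ≈ Φ{[r/2 − 1.991 × SD√(1.3/40)] / [SD√(0.7/40)]}

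- SD 50%, r 50%: (25 − 17.95)/6.614 = 1.07, rate 0.86
- SD 100%, r 50%: (25 − 35.89)/13.23 = −0.82, rate 0.21
- SD 100%, r 100%: (50 − 35.89)/13.23 = 1.07, rate 0.86
- SD 100%, r 25%: (12.5 − 35.89)/13.23 = −1.77, rate 0.04

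Simulation gives 85%, 21 to 22%, 85% and 4%.

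*Paired t test.* Standardised effect = (r/2)/(SD√(1 − ρ)):

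| SD | Rise r | r/2 | Standardised effect | Paired rate | Independent rate (simulated) |
|---|---|---|---|---|---|
| 50% | 50% | 25 | 0.598 | 96% | 85% |
| 100% | 50% | 25 | 0.299 | 45% | 21% |
| 100% | 100% | 50 | 0.598 | 96% | 85% |
| 100% | 25% | 12.5 | 0.149 | 15% | 4% |

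The independent test gives lower rates because it ignores the positive correlation between sites in one person and so overstates the standard error.

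**Site by site.** Comparing HT3 with LU5 in the Heart session by the independent test, at correlations 0 and 0.5, a rise of 0.5 SD gives 60% and 64%, and a rise of 1 SD gives 99% or more.

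**Midpoints only.** Under the same assumption of no effect away from the heated point, a paired comparison of the midpoints stays at about 5% for rises of 0 to 2 SD. That is a check on the arithmetic. It does not show that heat stays local.

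**The case against.** The strongest reply is that the plan never commits to the comparison examined here. It defines no two-site average and no same- versus other-meridian test. A reader might infer that the heated point is declared evidence for the treated meridian. The documents do not say so: the relevant sites are left undefined, and heated-site PU is legitimate data for objective 1, which is to describe microcirculation. This stands, and it limits the point to what the plan fails to prevent. It does not remove the point: the heated acupoint is a listed recording site, the outcome wording excludes nothing, and under section 2.5 the statisticians are unaware of the protocol, so they cannot set that site aside unless the SAP tells them to.

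Second, the rise, SD and correlation are all assumed, and with a small rise and a large SD the named test shows no excess over 5%. This also stands, so no single rate should be quoted as the trial's error rate.

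Third, the midpoints already allow a better test. True, but no text makes them the test. Nor can they be called unheated: the documents give no heat field or skin temperature, and section 2.6.1 places both elbow acupoints at the level of the cubital crease. Each midpoint lies on the line from its own elbow acupoint and may be nearer that heat source than the other.

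**Conclusion.** The point holds as a gap in outcome and analysis definition: nothing in section 3 or SAP 2.3 keeps direct local heating out of a same- versus other-meridian comparison. For the two-site comparison, the assumed scenarios give false-positive rates from 4% to about 85% with the named test and from 15% to 96% with a paired test, against a nominal 5%. These rest on the assumed rise, SD and correlation and on no effect elsewhere, and apply only if the heated point enters the comparison.

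The scope is the 40 people in the healthy intervention group. A reader might infer that the whole study is compromised. It is not: the COPD versus healthy control comparison, which serves the meridian-visceral question, involves no moxibustion. The change is worth making before analysis, since it is cheap and uses data already planned.

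**What to change.** In section 3 and SAP 2.3, for the healthy intervention group:

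1. Base the surface-surface specificity test on the two forearm midpoints only. For each, take the change from the 5-minute pre-moxibustion recording to a named later period. Compare, within person, the session treating that midpoint's own meridian with the session treating the other. Averaging the two differences gives one value per person and cancels any session effect common to both midpoints.
2. Report the heated acupoint separately as a description of local response, outside every same- versus other-meridian average or test.
3. State the limitation: a positive midpoint contrast cannot fully rule out spread of heat or a local vascular response, because each midpoint may be nearer its own heat source.

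The cost is wording only, with no change to procedures or recordings. In each session the heated channel, and the other elbow point with it, no longer counts toward the specificity claim.

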1.2.2 Inclusion criteria for health volunteers

(1) Healthy volunteers who could provide a recent medical examination report to confirm they have not any cardiovascular, respiratory, digestive, urinary, hematological, endocrine and neurological disease;

(2) $\text{age} \geq 20$ years, male or female;

(3) Participants have clear consciousness and could communicate with others normally;

(4) Participants could understand the full study protocol and have high adherence. Written informed consent is signed by themselves or their lineal kin.

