2.1 Study design

This is a prospective and open-label clinical trial. The time frame of the trial ranges from July 2019 to December 2020. A total of 120 participants will be divided into the healthy control group, COPD group and healthy intervention group., with 40 in each group respectively.

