2.2 Sample size estimation

This project is a clinical research using laser doppler to assess the biological characteristics of this meridian phenomenon. It belongs to meridian researches. Compared with general clinical trials, there is no unified standard for the sample size estimation. Based on similar studies conducted in China and foreign countries, as well as the consideration of the actual research conditions of this study, we planned to enroll a total of 120 participants, which includes 40 COPD patients and 80 healthy volunteers.

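### SAP section 2.3 gives the COPD-versus-healthy comparison no age or sex adjustment and does not say whether the intervention group's pre-moxibustion HT3 and LU5 recordings may support it

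*Combined protocol and SAP*

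**What the plan says.** - **Groups.** Part 2, section 2.1 has 120 participants "divided into the healthy control group, COPD group and healthy intervention group., with 40 in each group respectively". No method of allocating healthy volunteers between the two healthy groups is described.
- **Size.** Section 2.2 gives no effect size, SD or power. It remarks that "there is no unified standard for the sample size estimation" and settles on 40 COPD patients and 80 healthy volunteers.
- **COPD and healthy control recordings (section 2.6.3).** The sites are HT7, HT3, LU9 and LU5: "The blood flow curve and PU will be recorded for 5 minutes".
- **Healthy intervention recordings (section 2.6.3).** The sites are HT3, LU5 and the midpoints of the two meridians along the left forearm, in two sessions at least one day apart: "The measuring time points include 5 minutes before moxibustion, 15 minutes during moxibustion and 5 minutes after stopping moxibustion".
- **Common conditions.** The device, the 15-minute supine rest, the room conditions (section 2.6.2) and the limits on food, drink, smoking and exercise (section 2.6) apply to everyone.
- **Eligibility.** One set of criteria covers both healthy groups (section 1.2.2, beginning "Healthy volunteers who could provide a recent medical examination report"), with a minimum age of 20 and no upper limit. COPD patients must be 35 to 75 (section 1.2.1).
- **Analysis.** SAP section 2.3 specifies an independent-sample t test for numerical variables, a non-parametric test if the distribution is not normal, and "A P value < 0.05 will be considered statistically significance". It mentions no covariates and does not say which groups, sites or periods are compared.

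**The concern.** The meridian-visceral question rests on comparing resting perfusion in COPD patients and healthy people. Two things are missing from the plan for that comparison.

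First, the age ranges differ by design and nothing corrects for it. An unadjusted t test would attribute any age or sex difference in skin perfusion to COPD.

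Second, the study will hold a second set of resting recordings in healthy people at one Heart and one Lung point, and the SAP does not say what to do with them. If their use is not settled in advance, they will either go unused or be brought in after the results are known. The same two points give a Lung-minus-Heart difference within each person. That difference bears directly on the site-specificity aim and could be computed in all 120 participants, but the SAP does not mention it.

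**Working it through.** **The plan's own figure.** The total adds up: 40 + 40 + 40 = 40 + 80 = 120. It cannot be derived further, because section 2.2 gives no effect size, SD or power.

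**Inputs.** The group sizes are 40, 40 and 40 (section 2.1) and alpha is 0.05 (SAP section 2.3). Assumptions: two-sided testing, equal SDs, one value per person, and exchangeable healthy groups. Effects are in SD units because the documents give no SD.

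**Standard error.** SE = SD × √(1/n₁ + 1/n₂).

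- 40 v 40: √(1/40 + 1/40) = √0.05 = 0.2236 SD
- 40 v 80: √(1/40 + 1/80) = √0.0375 = 0.1936 SD
- Ratio: √(0.0375/0.05) = 0.866, a fall of 13.4%
- Equivalent equal groups: 2/(1/40 + 1/80) = 53.3 per group

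**Detectable difference at 80% power** = (1.960 + 0.842) × SE, and **power**, with the noncentral-t values alongside:

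| | 40 v 40 | 40 v 80 |
|---|---|---|
| Detectable difference, normal (t) | 0.626 (0.634) SD | 0.543 (0.547) SD |
| Power at 0.4 SD, normal (t) | 43.2% (42.4%) | 54.2% (53.5%) |
| Power at 0.5 SD, normal (t) | 60.9% (59.8%) | 73.3% (72.6%) |
| Power at 0.6 SD, normal (t) | 76.5% (75.5%) | 87.3% (86.7%) |

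**Unequal SDs.** If the healthy SD is k times the COPD SD, the SE ratio is √((1 + k²/2)/(1 + k²)). This is 0.949 at k = 0.5 and 0.775 at k = 2, so the SE falls by 5% to 23%. The range of k is an assumption.

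**Cost if the healthy groups differ.** Let their resting means differ by b SD. Pooling equal numbers shifts the healthy mean by b/2. For the COPD minus healthy control difference, in SD² units:

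- Mean squared error, 40 v 40: 0.05
- Mean squared error, pooled: 0.0375 + b²/4
- Pooling is better only if b² < 4 × (0.05 − 0.0375) = 0.05, that is b < 0.22 SD

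**Would the data reveal such a difference?** Comparing the two healthy groups, 40 v 40, at b = 0.22 gives 0.22/0.2236 = 0.98 standard errors, or about 17% power. If b were 0.5 SD and COPD equalled the healthy controls, the pooled test would be off by 0.25/0.1936 = 1.29 standard errors and would reject about 25% of the time instead of 5%. These values of b are illustrative; the documents give none.

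**Sites.** HT7 and LU9 are not recorded in the intervention group, so they stay at 40 v 40.

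**The case against.** A reader might infer that the plan compares COPD with only 40 healthy people and throws the other 40 away. The documents do not say so. SAP section 2.3 names no contrast and excludes no data; that reading comes from the group labels alone. What is documented is silence.

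A reader might also infer that a 40 v 80 comparison should become the main analysis. The case against that is strong, and most of it stands:

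- **The recordings are not shown to be interchangeable.** The left forearm is named only for the intervention group's midpoints, and no side is given for COPD patients or controls. The study is open-label, so intervention participants know moxibustion will follow. The second-session baseline comes after an earlier moxibustion session.
- **Exchangeability is assumed.** No randomisation between the healthy groups is mentioned, and the comparison of those groups has little power to expose a difference large enough to matter.
- **The power figures are for an unadjusted comparison.** In an age-adjusted model the gain depends on the ages of the added volunteers. People well outside 35 to 75 add less and lean more on the model's form.
- **Unequal control numbers could mislead.** With 80 controls at the elbow and 40 at the wrist, significance at HT3 or LU5 but not at HT7 or LU9 could reflect numbers alone.
- **A separate control group measured at all four sites is a legitimate design.**

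None of this removes the need for age and sex adjustment, which applies equally to 40 v 40, or the need to decide in advance how the extra baselines are used.

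**Conclusion.** The point holds as an inexpensive improvement; it is not an error that invalidates the comparison. The SAP should name the COPD contrast, adjust it for age and sex, add the within-person Lung-minus-Heart difference, and settle the role of the intervention baselines.

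The benefit of pooling is moderate and conditional: a 13% smaller standard error at HT3, LU5 and their difference (each in units of its own SD), if the healthy groups are exchangeable with equal SDs and the same side is measured. It narrows the interval but does not remove confounding, and beyond a difference of about 0.22 SD between the healthy groups it does more harm than good. That supports a supplementary role only. The size of any age confounding cannot be computed from the documents, since they give no perfusion data by age.

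**What to change.** In SAP section 2.3:

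1. **Main comparison.** State it as COPD (40) versus healthy control (40) at each of HT7, HT3, LU9 and LU5, from a linear model adjusted for age and sex as recorded at screening (Part 2, section 2.3). State how non-normal data will be handled while keeping the covariates, for example by log-transforming PU.
2. **Site specificity.** Add the within-person LU5 minus HT3 difference as a Lung-versus-Heart contrast, compared between the same two groups with the same adjustment.
3. **Supplementary analysis.** Prespecify the same adjusted model at HT3, LU5 and LU5 minus HT3 for COPD (40) versus all healthy volunteers (80). Use one value per intervention participant, from the first-session pre-moxibustion recording, and only if the measured side is confirmed to be the same in all groups.
4. **Reporting.** Show the two healthy groups' resting values, ages and sexes side by side, with the difference between the groups and its confidence interval. Do not treat a non-significant difference as proof that pooling is safe. Do not contrast the pooled elbow results with the unpooled wrist results by significance.

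The cost is a few sentences in the SAP, covariates already collected, and one further model. No one extra is enrolled and no recording is added. The measured side should be written into section 2.6.3 for every group; if it differs between groups, the supplementary analysis is dropped and the rest of the fix is unaffected.
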